9. RESEARCH METHODS

9.1 STUDY DESIGN

A retrospective analysis will be done based on a claims dataset delivered by two German sickness funds (so far, a cooperation with [REDACTED] is planned, second sickness fund needs to be named yet). The dataset will cover the period 01/01/2013-30/06/2018⁷. In selected analyses, incident COPD patients will be observed for an exact follow-up period of 12 months (in subgroup analyses: 24 and 36 months); censoring of patients will only be done in case a patient died during the respective follow-up period. [REDACTED]

The data will be analyzed for a pre-index period (12 months before index diagnosis) and for a follow-up period of 12 months after index date. In subgroup analyses, longer follow-ups (24 and 36 months, and full observation time (up to 54 months⁸)), are used. Death after index diagnosis during the follow-up is the only accepted exception from this rule. For a subsample of patients, disease management program (DMP) data might be available. These provide disease specifics such as forced expiratory volume in 1 second (FEV₁) values, specifics of prescribed therapy, and exacerbation frequency and severity.

The dataset contains available information on the sociodemographic characteristics of the patients, their treatment with prescription aids and medications, their outpatient and inpatient treatment, and COPD-specific clinical parameters for the patients who participated in a disease management program (DMP). A first overview of data generally available in claims data of a German sickness fund is given in Table 1. The study-specific data set (required data according to approved study protocol) needs to be approved by the respective sickness funds, based on the study objectives and the respective methodology as outlined in this protocol.

⁷ If more data will be available until time of analysis start, further quarters (from 2018) will be included into the analysis.

⁸ If more data will be available until time of analysis start, further quarters (from 2018) will be included into the analysis.

[figure not shown]
Table 1 Data generally available in the claims data set

Sociodemographic characteristics	Inpatient care	Outpatient care	Outpatient medication (prescriptions only)	Other data

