9.3.2 Outcomes

9.3.2.1 Primary outcomes

The primary objective of this study is to describe the real-life drug treatment of patients with incident COPD, including description of treatment sequence/escalation in the first 12/24/36 months after incident diagnosis. This analysis will be based on the following samples:

- COPD-12: All incident COPD patients with a follow-up of 12 months since index date (analysis will be done for the first 12 months of observation)
- COPD-24: All incident COPD patients with a follow-up of 24 months since index date (analysis will be done for the first 24 months of observation)
- COPD-36: All incident COPD patients with a follow-up of 36 months since index date (analysis will be done for the first 36 months of observation)
- COPD FULL DATA: All incident COPD patients. (analysis will be done for the full observation period)
- COPD DMP-12: All incident COPD patients with available DMP data (at least one entry after index date) and a follow-up of 12 months since index date (analysis will be done for the first 12 months of observation)

In this analysis, baseline treatment as well as treatment cascades including mean duration of treatment in the pre-defined follow-up periods will be assessed. Results will be reported as follows:

- Mean number of different agents an observed patient received (per patient year)¹³
- List of most frequently prescribed agents (based on [Suppl. Table 2](#)) including percentage of patients who received these agents
- Longitudinal analysis of treatment patterns/cascades with long-acting bronchodilators and ICS, as described in [Table 2](#). Here, proportion of observed patients whose treatment can be described by the pre-defined treatment patterns will be assessed.

Table 2

Description of treatment patterns/cascades (template for reported outcomes)^{14,15}
(please note: below table might not show all theoretically possible treatment patterns. In the analysis, based on observed treatment patterns, all treatment pattern combinations that were observed in >5% of the patient population will be reported)

Therapy pattern after index date	1st line	2nd line	3rd line	4th line	N (%) of patients
Mono, no switch during follow-up period	LAMA	-	-	-	...
	LABA	-	-	-	...
	ICS	-	-	-	...
Mono, with switch	LAMA	LABA	-	-	...
	LAMA	ICS	-	-	...
	LABA	LAMA			
	LABA	ICS			
	ICS	LABA			
	ICS	LAMA			

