
Description of treatment patterns/cascades (template for reported outcomes)
(please note: below table might not show all theoretically possible treatment patterns. In the analysis, based on observed treatment patterns, all treatment pattern combinations that were observed in >5% of the patient population will be reported)

Therapy pattern after index date	1st line	2nd line	3rd line	4th line	N (%) of patients
Triple therapy, de-escalation during follow-up	LAMA+LABA+ICS	LAMA+LABA LAMA+ICS LABA+ICS			...
Dual therapy, any downgrading during follow-up	LABA+ICS LABA+ICS LAMA+ICS LAMA+ICS LABA+LAMA LABA+LAMA	LABA ICS LAMA ICS LABA LAMA			

Others

For the most common Top-5 treatment cascades, duration of treatment of each line of therapy as well as characteristics of patients that could be assigned to the specific cascades will be reported.

Please note that a specific combination therapy will be assumed to have been prescribed if there was a prescription of a respective combination agent. In case separate agents were prescribed, two scenarios are applied: (1) A combination treatment is assumed to have been prescribed if the respective agents were prescribed at the same day or (2) a combination treatment is assumed to have been prescribed if the respective agents were prescribed within a 21 days window and a similar prescription behavior was repeated at least one additional time (example – assumed LABA+LAMA combination: LABA prescription day 1,

LAMA day 10, LABA day 91, LAMA day 96). Coverage calculation (days covered by a respective treatment pattern) will be based on the defined daily dosage (DDD) of each prescription.

An agent will be considered as discontinued if a supply gap of at least 60 days (sensitivity analysis: 15/30/90 days) is observed.

In an additional Kaplan Meier analysis, time to start of a dual therapy (LAMA+LABA/LABA+ICS/LAMA+ICS) and time to start of a triple therapy (LAMA+LABA+ICS) will be assessed (days from incident diagnosis until first day of triple

therapy). This analysis will be based on the COPD full data sample, i.e. no fixed follow-up period but patient-specific follow-up periods (until end of observational period or until censoring or until date of event, whatever comes first) will be applied.

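### Treatment duration is averaged inside fixed 12/24/36-month windows with no rule for lines still running, and no visible analysis measures time on a line

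*Combined protocol and SAP*

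**What the plan says.** Section 9.3.2.1 (Primary outcomes) says that "treatment cascades including mean duration of treatment in the pre-defined follow-up periods will be assessed". Each fixed sample is limited to its own window; for COPD-12, "analysis will be done for the first 12 months of observation", with matching wording for 24 and 36 months. COPD FULL DATA is also listed, over the full observation period.

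After Table 2, line-level duration is added: "For the most common Top-5 treatment cascades, duration of treatment of each line of therapy" is to be reported, with no estimator named. The rule for an end is "An agent will be considered as discontinued if a supply gap of at least 60 days", with 15, 30 and 90 days as sensitivity analyses.

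Section 9.1 states, for the analyses with exact follow-up, that "censoring of patients will only be done in case a patient died during the respective follow-up period".

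The Kaplan-Meier analysis in 9.3.2.1 is on COPD FULL DATA: "time to start of a dual therapy (LAMA+LABA/LABA+ICS/LAMA+ICS) and time to start of a triple therapy (LAMA+LABA+ICS) will be assessed". Table 4 adds a Kaplan-Meier analysis of time to escalation to a therapy that includes ICS. Section 9.7.1 allows further Kaplan-Meier curves where suitable, and its next sentence is partly redacted. It also gives median, range, SD and confidence interval for continuous data.

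**The concern.** A reader will take duration of a line to mean how long patients stay on that regimen. Two features of the plan prevent that reading.

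- **Truncation.** A line still running at month 12 contributes only the time seen so far. If that time enters the mean as a completed duration, the mean falls below true persistence. The shortfall grows with true persistence and with later line start.
- **Conditioning on the outcome.** Table 2 sorts patients by what happened during follow-up. A patient on LAMA who adds LABA in month 14 is a non-switcher in COPD-12 and a switcher in COPD-24. First-line duration in a switching row therefore comes only from those who switched before window end.

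Treatment sequence is the primary objective. Durations affected in these ways cannot be compared across the three windows, or between first lines overall and later lines, as measures of persistence.

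**Working it through.** **Figures in the plan.** It gives no figure for duration or persistence. The nearby figures reproduce: 0.65 × 40,000 = 26,000 users of long-acting bronchodilators. Index dates from 01/01/2014 to 30/06/2017 with data to 30/06/2018 give 12 to 54 months of possible follow-up.

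**Assumptions, not in the documents.** Time on a line is exponential with true mean m = 6, 12 or 24 months, the line starts s months after index, and running lines are cut at window end W.

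**Step 1: windowed mean.** E[min(T, W−s)] = m(1 − exp(−(W−s)/m)); the share still running is exp(−(W−s)/m). Example with m = 12, W = 12, s = 0: 12 × (1 − e⁻¹) = 7.6 months, with 37% still running.

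| True mean (months) | 12-month window | 24-month window | 36-month window | Still running at month 12 |
|---|---|---|---|---|
| 6 | 5.2 (86%) | 5.9 (98%) | 6.0 (100%) | 14% |
| 12 | 7.6 (63%) | 10.4 (86%) | 11.4 (95%) | 37% |
| 24 | 9.4 (39%) | 15.2 (63%) | 18.6 (78%) | 61% |

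These are for s = 0; percentages are of the true mean. With m = 12 and W = 12, starts at month 0, 3, 6 and 9 give 7.6, 6.3, 4.7 and 2.7 months.

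**Step 2: first line among in-window switchers.** Let T now be the time to switch, starting at index. Then E[T | T < W] = m − W/(exp(W/m) − 1). For m = 12, W = 12: 12 − 12/(e − 1) = 5.0.

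| True mean (months) | 12-month window | 24-month window | 36-month window |
|---|---|---|---|
| 6 | 4.1 | 5.6 | 5.9 |
| 12 | 5.0 | 8.2 | 10.1 |
| 24 | 5.5 | 10.0 | 13.7 |

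In the 12-month window, a fourfold range of true persistence (6 to 24 months) shows up as 4.1 to 5.5 months.

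**Step 3: does censoring running lines help?** A simulation of 26,000 lines, with starts uniform over months 0 to 9 and no deaths, gives for the 12/24/36-month windows:

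- True mean 12 (true median 8.3): uncensored mean 5.4/9.5/11.0; uncensored median 5.1/8.2/8.2; Kaplan-Meier median 8.1/8.2/8.2.
- True mean 24 (true median 16.6): uncensored mean 6.3/13.3/17.5; uncensored median 6.2/15.4/16.4; Kaplan-Meier median not reached/16.4/16.4.

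Censoring recovers the median wherever follow-up is long enough. An ordinary median also does well in the longer windows, but not in the 12-month window.

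**Step 4: the gap rule.** If supply ends in the last 60 of 365 days (60/365 = 16% of days), the gap cannot be completed inside COPD-12. As a share of in-window stops, with 60 days = 1.97 months and m = 18: (e^(−10.03/18) − e^(−12/18))/(1 − e^(−12/18)) = 0.059/0.487 = 12%. With m = 6 it is 6%. Most patients have later claims that could confirm the gap. The latest entrants, indexed on 30/06/2017, have none under the planned data end.

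**The case against.** The strongest defence is that the objective is explicitly treatment in the first 12, 24 and 36 months. A mean within those periods is then a valid restricted mean, and different values by window are expected. That stands, and it is why the mean can be kept under a clear label. It is also true that no sentence says running lines are cut. This is inferred from the window wording, although no other rule is given. COPD FULL DATA is analysed as well, but an uncensored mean there would still be cut at end of data, after 12 to 54 months. Medians help with truncation when fewer than half the lines are running. They do not cure the conditioning on switching.

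Stronger readings that a reader might infer, and that the documents do not support:

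- *Durations mainly reflect window length and start date.* This depends on unknown persistence. With a true mean of 6 months, a line from index is understated by only 0 to 2% in the 24- and 36-month windows.
- *Second lines look shorter than first lines within a cascade.* With equal exponential persistence, E[min(T₂, W−T₁) | T₁ < W] also works out to m − W/(exp(W/m) − 1), the same as for the first line. A difference appears only when non-switchers' first lines are pooled in.
- *Kaplan-Meier is planned only for dual and triple therapy.* Table 4 adds escalation to a therapy including ICS.
- *16% of stops cannot be confirmed.* That is a share of days, not of stops. Counting late stops as ongoing would also lengthen measured durations, not shorten them.
- *Time on a line is certainly not analysed.* The general Kaplan-Meier clause is followed by redacted text, and the contents list has a redacted entry after 9.7.1. One can say only that no visible text names it.

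**Conclusion.** The point holds as a gap in specification with a better method within reach. The plan makes windowed mean duration and cascade-level line duration primary outputs, states no handling for lines still running at window end, and does not visibly name an analysis of time on a line.

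If running lines are cut, the mean understates persistence. For a line from index, the shortfall in the 12-month window is 14%, 37% or 61% for true means of 6, 12 or 24 months. In the 36-month window it is 0%, 5% or 22%. These sizes rest on assumed exponential persistence; the direction does not. The conditioning in switching cascades does not depend on how running lines are cut and follows from the structure of Table 2. The change is advisable, since the description of which regimens patients receive is unaffected.

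**What to change.** In 9.3.2.1 and Table 4:

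1. Keep the mean, but label it 'days on therapy within the first 12/24/36 months' and state how lines running at window end are counted.
2. Add time from line start to the first of discontinuation (60-day gap, dated at supply end) or switch. Run it on COPD-FULL DATA, the sample the note to Figure 3 already assigns to time-to-event analyses. Present it by regimen and line number, pooled across cascades. Kaplan-Meier inside a switching cascade would not help, because every first line there ends in a switch by definition.
3. Censor at end of data and treat death as a competing event. Report the median where reached, and the share still on the line at 6, 12, 24 and 36 months.
4. Use claims after the 12/24/36-month mark to confirm gaps. Censor patients with less than 60 days of data after supply end, changing that limit to match the 15/30/90-day sensitivity analyses.
5. Present cascade-specific durations as descriptive only.

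The cost is wording and a few extra curves from data already held. Some medians may not be reached.

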9.3.2.2 Secondary outcomes

First Secondary

Comparison of initial drug treatment with treatment guidelines

Comparison of real-world treatment of patients with guidelines will be done based on two samples: COPD-12 and COPD DMP-12. Assessment will generally be done for two time points:

- For all patients at index date (+ 4 weeks)
- For patients who received a triple combination (LABA+LAMA+ICS) at first day of triple therapy prescription.

Prescription patterns will be compared with German treatment guideline recommendations. Here, the 2018 S2 guideline [1] will be used (sensitivity analysis: 2012 guideline, which is an updated version of the 2006 guideline [2]). Obviously, as patients are only observed until mid of 2018, it cannot be expected that they were treated in line with the 2018 S2 guideline. However, this analysis describes potential needs to adapt the current treatment of the patients in the future, and is as such important for preparation of later initiatives to optimize the treatment of the patients.

Based on claims data only, assessment of the severity of the COPD disease for COPD patients is hardly possible. The reason is that neither FEV₁ data nor symptoms' data as measured by the COPD assessment test (CAT) or the Modified Medical Research Council (mMRC) are available in a claims dataset. So, for the comparison of the real-world treatment with 2018/2012 guideline recommendations, based on sample COPD-12, the following analyses will be done:

- COPD-12, at index date
 - Based on the inclusion criteria, an incident COPD patient did not experience any exacerbation in the previous 12 months, as no such diagnosis was documented. So, the initial treatment with long-acting bronchodilators should generally not include use of ICS (both guidelines). Moreover, based on the 2012 guideline, a therapy with long-acting bronchodilators should start with either a LAMA or a LABA, but not with a combination of them.

So, based on these criteria, the following percentages will be reported:

- Percentage of patients not treated in line with 2018 guideline
 - Therapy at index date includes ICS
- Percentage of patients not treated in line with 2012 guideline
 - Therapy at index date includes ICS or a LABA/LAMA combination or triple therapy of LABA+LAMA+ICS¹⁶
- COPD-12, at first date of an observed LABA+LAMA+ICS combination, which is not the index date
 - According to both guidelines mentioned above, a triple combination treatment LABA+LAMA+ICS should only be prescribed if a patient experienced at least two exacerbations or one severe exacerbation requiring an inpatient treatment in the history of the disease. Based on this, the following percentage will be reported:
 - Percentage of patients not treated in line with the 2012/2018 guideline
 - Only 1 or less confirmed outpatient diagnoses and no inpatient diagnosis of a COPD exacerbation (ICD-10 J44.1) before date of prescription of a triple therapy.
- COPD-12, for the whole follow-up period (12 months)
 - A treatment intensification (mono to dual therapy, mono to triple or dual to triple therapy) should generally be accompanied by a thorough application of recommended diagnostic measures, according to the 2012/2018 guidelines. For these, typically, general practitioners (GPs) do not have the necessary infrastructure. Based on this, the following percentage will be reported:
 - Percentage of patients who received a treatment intensification without any previous visit of a pneumologist or hospital (same quarter or previous quarter)

Sensitivity analysis

In a first sensitivity analysis, those of above patients will be included for whom at least one ICD-10 COPD code that provides information up to the 5th level is documented: These subcodes include information about FEV₁ level. For patients for whom such a subcode is available, in this analysis, disease severity will be defined based on this information, which is mainly important when applying the 2012 guideline.

¹⁶ Of those patients starting with triple therapy of LABA+LAMA+ICS at time of incident COPD diagnosis, physician visits (separately of cardiologists, pneumologists) and measures of lung function (DMP-dataset only) before or at index date will be reported. Time since last physician visits to a cardiologist or a pneumologist will be reported too.

In a second sensitivity analysis, the sample COPD DMP-12 will be analyzed. In the DMP data set, additional documentation about exacerbation history and FEV₁ is available. Based on these data, the following analyses are planned:

- COPD DMP-12, at index date: no additional analysis, as DMP data will not be available for the pre-index period
- COPD DMP-12, at first date of an observed LABA+LAMA+ICS combination, which is not the index date; patients for whom at least one DMP entry before date of prescription of above combination will be included
 - According to both above guidelines, a triple combination treatment LABA+LAMA+ICS should only be prescribed if a patient experienced at least 2 exacerbations or one severe exacerbation requiring an inpatient treatment in the history of the disease. In addition, the 2012 guideline also recommended such a treatment in case a FEV₁<50% could be observed. Based on this, the following percentages will be reported:
 - Percentage of patients not treated in line with the 2018 guideline
 - Only one or no confirmed outpatient diagnosis and no inpatient diagnosis of a COPD exacerbation (ICD-10 J44.1) before date of prescription of a triple therapy.
 - Percentage of patients not treated in line with the 2012 guideline
 - Only one or no confirmed outpatient diagnosis and no inpatient diagnosis of a COPD exacerbation (ICD-10 J44.1) and only one or no outpatient diagnosis and no inpatient exacerbation diagnoses as documented in the DMP dataset and no documented FEV₁ value <50%.

Second Secondary

Description of exacerbation frequency

For all samples (COPD-12, COPD-24, COPD 36, COPD DMP-12, COPD DMP-24, COPD DMP-36, COPD-FULL DATA), exacerbation frequency in the pre-defined follow-up periods (12 months, 24 months, 36 months, patient-individual follow-up times) will be described. Because of the higher diagnosis validity, in the main analysis only severe exacerbations leading to an inpatient hospitalization (COPD exacerbation documented as main diagnosis: ICD-10 J44.1) will be considered. Moreover, in a separate analysis proxies will be used to estimate non-severe exacerbations. Therefore prescriptions of SCS/OCS either separately or in combination with antibiotics, will be considered as proxy for the treatment of a non-severe exacerbation (without an inpatient hospitalization). Exacerbation frequency (once for severe and once for non-severe exacerbations) will be reported as percentage of patients having experienced at least 1 exacerbation, exactly 1 exacerbation, exactly 2 exacerbations, exactly 3 exacerbations, and >3 exacerbations, and as mean number of exacerbations per observed patient-year.

Third Secondary

Description of health care resource use and direct treatment cost

Health care resource use (HCRU) and direct cost will be reported as described in Table 3, based on the perspective of a German sickness fund and based on prices of the respective years as reported in the claims data base. HCRU and cost will be reported for the following samples in separate analyses: COPD-12, COPD-24, and COPD-36.

Generally, HCRU/cost will be reported per observed patient year. HCRU and cost will be compared between the following patient groups:

- Patients participating in a DMP versus those who did not participate
- Patients having received early (first 3 months after index date) a triple combination therapy (LABA+LAMA+ICS) versus those who did not.

[figure not shown]
In a separate analysis based on COPD-36 sample, cost during the first year after incident COPD diagnosis will be compared with costs in the second and third year after incident diagnosis.

[figure not shown]
[figure not shown]
Table 3 HCRU and direct healthcare cost definition

Item	HCRU	Cost
COPD medication	
• Nb. of prescriptions for medications as reported in Suppl. Table 2, per agent type• Nb. of prescribed DDDs for medications as reported in Suppl. Table 2, per agent type	
• Drug cost (based on list prices) for medications as reported in Suppl. Table 2.
Other medications	
• Nb. of non COPD-medications, defined as at least 2 prescriptions of an agent (on third level of ATC groups)• Antibiotics for systemic use (ATC J02AA) and antibiotics in combination with corticosteroids (ATC D07C)	
• Drug cost of prescribed non-COPD medications
Outpatient treatment	
• Nb. of GP visits• Nb. of pneumologist visits• Nb. of other outpatient specialist visits	
• Cost of outpatient visits as defined in the HCRU column, based on the proxy of “treatment points”
Hospitalizations	
• Nb. of hospitalizations with a COPD-exacerbation (J44.1) including mean duration of stay in days• Nb. of hospitalizations with any COPD diagnosis as main diagnosis (J44.-) including mean duration of stay• Other non-COPD hospitalizations including mean duration of stay in days• Time to first all-cause hospitalization	
• Cost for hospitalizations as defined in the HCRU column
Long-Term Oxygen Therapy (LTOT) ¹⁷	
• Number of patients who received LTOT• Mean/median time from incident COPD diagnosis until start of LTOT for those patients	
• Cost for LTOT

¹⁷ J96.1, Z99.0, Z99.1, Z99.8, Z99.9, Z46.8, Z46.9 (ICD-10-GM-2018); 8-712.1, 8-713.0, 8-716 (OPS 2016)

001-MCS-90-124_RD-01 (4.0)

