9.2 SETTING

An anonymized dataset from the cooperating sickness funds, which includes all patients with at least one COPD diagnosis, who were insured by this sickness funds for the entire period (01/01/2013 - 30/06/2018) will be available.

A patient will be confirmed as being COPD-incident if specialists documented at least two confirmed outpatient COPD diagnoses (ICD J44.-) and/or at least one inpatient COPD diagnosis (ICD J44.-), without such diagnoses in the previous 12 months and without any COPD prescription in the previous 12 months (Suppl. Table 2).

Specific inclusion criteria can be described as follows:

- All patients should have been covered by the sickness fund for the entire period (01/01/2013-30/06/2018) or, in case a patient deceased after index date, for the time until death
- A patient will be included as an incident COPD patient if either a hospital documented at least one COPD diagnosis (ICD-10 J44.-) or a specialist (pneumologist) documented at least two confirmed COPD diagnoses (above ICD-10 code) in two different quarters; the first of the above diagnoses is defined as index diagnosis; inclusion period is defined as lasting from 01/01/2014 until 30/06/2017

- Patients should not have received any COPD diagnosis (ICD-10 J44.-) or any COPD-associated medication (Suppl. Table 2)⁹ in the 12 months pre-index period
- Patient should have, at date of incident COPD diagnosis (index date), an age of at least 40 years

Patients who received at least one confirmed inpatient asthma diagnosis or two confirmed outpatient diagnoses of asthma (ICD-10: J45.-) by pneumologists after the incident COPD diagnosis (index diagnosis) will be separately observed.

Based on these inclusion/exclusion criteria, the following data sets will be analyzed (Figure 3)¹⁰:

- COPD-FULL DATA: All incident COPD patients with a follow-up of up to 54 months
- COPD-12: All incident COPD patients with a follow-up¹¹ of 12 months since index date
- COPD-24: All incident COPD patients with a follow-up of 24 months since index date
- COPD-36: All incident COPD patients with a follow-up of 36 months since index date
- COPD DMP-FULL DATA: All incident COPD patients with available DMP data (at least one entry during 3 months after index date¹²) and a follow-up of up to 54 months.
- COPD DMP-12: All incident COPD patients with available DMP data (at least one entry during 3 months after index date) and a follow-up of 12 months since index date

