- COPD DMP-24: All incident COPD patients with available DMP data (at least one entry during 3 months after index date) and a follow-up of 24 months since index date
- COPD DMP-36: All incident COPD patients with available DMP data (at least one entry during 3 months after index date) and a follow-up of 36 months since index date.

⁹ Prescription of systemic/oral corticosteroids (SCS/OCS) will not be considered as exclusion criteria

¹⁰ Please note that this samples will not include patients with at least one confirmed inpatient or two confirmed outpatient diagnoses of asthma (ICD-10: J45.-) by pneumologists after the incident COPD diagnosis (index diagnosis) during the follow-up period. Those patients will be described separately.

[figure not shown]
¹¹ Time since patient-individual index date until 30/06/2018; patients who died within this period will not be excluded from the analysis

¹² So far it is unknown how many patients were included in the DMP directly after incident diagnosis and for how many patients an entry in the first months after diagnosis will be available. Thus, depending on the pattern that will be observed in the data, the restriction „at least one entry during the 3 months after index date“ might be extended to „at least one entry during the 6/12 months after index date“.

Figure 3

Baseline period, inclusion period, follow-up period for different study samples

(note: for time to event analyses, COPD-full data sample (with full follow-up times) will be applied). DMP: disease management program (refers to the subsample of patients who participate in the COPD DMP and thus provide more detailed data)

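### The index-date guideline rule ignores a J44.1 index admission and overlaps in time with the triple-therapy rule, so the two can disagree on early triple therapy

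*Combined protocol and SAP*

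**What the plan says.** Entry (Section 9.2): a patient qualifies if "either a hospital documented at least one COPD diagnosis (ICD-10 J44", any subcode, or through two confirmed pneumologist diagnoses in different quarters; "the first of the above diagnoses is defined as index diagnosis". No J44 code and no COPD medication is allowed in the 12 months before index. Footnote 9 makes one exception: "Prescription of systemic/oral corticosteroids (SCS/OCS) will not be considered as exclusion criteria".

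Index-date rule (Section 9.3.2.2, First Secondary, COPD-12): the time point is "For all patients at index date (+ 4 weeks"). The stated reason for treating ICS at the start as a deviation is that "an incident COPD patient did not experience any exacerbation in the previous 12 months, as no such diagnosis was documented". Therapy with any ICS is then scored not in line with the 2018 guideline. Therapy with ICS, a LABA/LAMA combination or triple therapy is scored not in line with the 2012 guideline. Neither score depends on exacerbation status.

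Triple-therapy rule (same section): it applies at the first LABA+LAMA+ICS date other than the index date. Under both guidelines triple therapy is accepted only "if a patient experienced at least two exacerbations or one severe exacerbation requiring an inpatient treatment in the history of the disease". It is scored not in line when at most one outpatient and no inpatient J44.1 diagnosis precedes it.

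Exacerbation outcome (Section 9.3.2.2, Second Secondary): a severe exacerbation is a hospitalisation with "COPD exacerbation documented as main diagnosis: ICD-10 J44.1". In a separate analysis, "prescriptions of SCS/OCS either separately or in combination with antibiotics, will be considered as proxy for the treatment of a non-severe exacerbation".

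**The concern.** The premise of the index-date rule follows from the selection rule and is not an observation about the patients. It also stops at the day before index. A patient can enter the cohort through an admission that the plan's own outcome definition counts as a severe exacerbation, and the index rule has no place for that.

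The second assessment does take such an admission into account, and the two assessments are not clearly separated in time. At stake is a named secondary objective, the share of patients treated in line with the 2012 and 2018 guidelines. For some patients the answer depends on which rule is read, or on whether a prescription fell on day 28 or day 29. The planned sensitivity analyses do not repair this. The first uses FEV₁ subcodes, and the second states that nothing further is done at index date. Footnote 16 describes physician visits and lung-function measures in patients who start on triple therapy, but not their exacerbation status.

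**Working it through.** The plan states no figure on this point, so the check is to apply both rules as written.

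1. *Can the index event be an exacerbation?* J44.1 lies within J44.-, one hospital diagnosis suffices, and the first qualifying diagnosis is the index. So yes. When J44.1 is the main diagnosis, the Second Secondary outcome counts the stay as severe.

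2. *Can it precede a triple prescription scored at index?* The index assessment covers days 0 to 28 (4 weeks × 7 days). Table 1 in Section 9.1 lists outpatient prescriptions only. After an index admission, the first visible prescription will therefore tend to fall after day 0, particularly if the index date is the admission day, which the plan does not state.

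3. *Apply both rules to a first LABA+LAMA+ICS on days 0, 1, 10, 28 and 29.* Days 1, 10 and 28 behave alike. Reading A takes the words excluding the index date literally (day 0 only). Reading B takes them to mean the whole four-week window.

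| Coded history before the triple | Day | Index rule (2012 and 2018) | Triple rule, reading A | Triple rule, reading B |
|---|---|---|---|---|
| J44.1 admission is the index | 0 | not in line | not applied | not applied |
| | 1–28 | not in line | **in line** | not applied |
| | 29 | not applied | in line | in line |
| Two outpatient J44.1 | 1–28 | not in line | **in line** | not applied |
| | 29 | not applied | in line | in line |
| One outpatient J44.1 is the index | 1–28 | not in line | not in line | not applied |
| | 29 | not applied | not in line | not in line |
| Steroid courses only, no J44.1 | 1–28 | not in line | not in line | not applied |
| | 29 | not applied | not in line | not in line |

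Under reading A the same prescription gets opposite scores on days 1 to 28. Under reading B nothing is scored twice, but the patient with the J44.1 index moves from not in line on day 28 to in line on day 29. The last block shows that steroid-treated episodes alone never produce the conflict, because the triple rule counts only J44.1 diagnoses.

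4. *Size.* The documents give neither the share of patients indexed on a J44.1 admission nor the share of those starting triple therapy on days 1 to 28. As an illustration only, assume 5% to 20% for each and take the 40,000 patients of Section 9.5:

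- low: 40,000 × 0.05 × 0.05 = 100 patients, 0.25 percentage points
- high: 40,000 × 0.20 × 0.20 = 1,600 patients, 4.0 percentage points

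This sixteenfold range reflects the assumptions and is not an estimate.

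**The case against.** Several points limit the reach of this, and most of them stand.

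- The premise refers only to the previous 12 months, and for coded diagnoses before index it is literally true. A reader might infer that the plan assumes patients never had an exacerbation; it does not say so. What it omits is the index event.
- A reader might infer that the 2018 index-date percentage falls with the premise. Figure 1 (Section 7) does not support that. For untreated patients with a hospitalised exacerbation it lists LAMA or LAMA + LABA, and ICS appears only under escalation or change. The 2018 score for ICS at index may therefore stand without the premise. This does not remove the conflict, because the triple rule accepts triple therapy after one inpatient exacerbation under the same guideline.
- The double scoring depends on reading A. The plan shortens the four-week time point to the index date elsewhere in the section, so reading B is plausible. The change between days 28 and 29 then remains.
- A reader might blame pre-index steroids for the opposite verdicts. They only weaken the premise. The plan uses the steroid proxy in a separate analysis of follow-up, and carrying it back to the year before diagnosis is a choice.
- A reader might count every J44.1-indexed patient as misclassified. Assuming 20% to 50% hospital-indexed and 20% to 40% of those J44.1 gives 4% to 20%, or 1,600 to 8,000 of 40,000. Both inputs are assumed, and the total includes patients with no ICS or LABA/LAMA in the four weeks, whom the index rule never marks as deviating.
- A reader might infer that the logistic regression on adherence is distorted. Table 4 does not name the adherence criterion used as its outcome, so this cannot be shown.

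**Conclusion.** The concern holds in a limited form. The justification for the index-date rule is a product of the entry criteria and does not cover a J44.1 admission that is itself the index diagnosis. For such patients with a first triple prescription on days 1 to 28, the two rules as written give opposite verdicts. On the more lenient reading of the index date, the verdict changes between day 28 and day 29. Two outpatient J44.1 diagnoses before the triple produce the same pattern.

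The contradiction follows from the text and needs no assumed number. The count of patients affected cannot be obtained from the documents, and the 100 to 1,600 shown above rests wholly on assumed shares. This should be corrected before analysis, because it changes what is reported for a secondary objective. It does not show that the index-date percentages are wrong overall.

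**What to change.** 1. Remove the absence of documented exacerbations as a justification for the index-date rule.
2. Flag patients whose index stay is coded J44.1, and report the 2018 and 2012 index-date percentages separately with and without the flag. Optionally, as a sensitivity analysis, also split by SCS/OCS prescriptions in the 12 months before index.
3. State that the index assessment covers days 0 to 28 and that the triple-date assessment starts after day 28, so that each prescription is judged once.
4. Have the sponsor reconcile Figure 1 in Section 7, the index-date rule, and the triple rule (in both the COPD-12 and COPD DMP-12 versions) for patients with a hospitalised exacerbation at index. This review does not choose the criterion. Step 3 alone would leave the change between days 28 and 29 in place, so step 4 is needed as well.

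Cost: protocol wording and one flag built from codes already in the dataset, plus slightly more tabulation. The share not in line may become less simple to state, or somewhat lower.
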